9.2.4 Definitions of Secondary Efficacy Endpoints

Real world Intracranial Objective Response Rate is defined as the proportion of subjects with a BOR of either CR or PR of intracranial disease, where BOR is the best response recorded from the start of treatment until disease progression or start of other anticancer therapy in real world setting. As per RECIST v1.1 guidelines, PR and CR do not need to be confirmed following initial response documentation.

Real world Objective Response Rate is defined as the proportion of subjects with a BOR of either CR or PR, where BOR is the best response recorded from the start of treatment until disease progression or start of other anticancer therapy in real world setting. As per RECIST v1.1 guidelines, PR and CR do not need to be confirmed following initial response documentation.

Real world Disease control rate is defined as the proportion of patients with complete response (CR) or partial response (PR) or subjects with stable disease (SD) as per investigator assessment according to RECIST 1.1 criteria in real world setting.

Overall Survival is defined as the time from start of treatment to the date of death for any cause. In the absence of confirmation of death, survival time will be censored at the last date the subject is known to be alive.

Real world Intracranial Time To Progression is defined as the time from randomization to the date of the first documentation of objective progression of intracranial disease, based on either new brain metastases or progression of existing brain metastases in real world setting.

9.2.5 Analysis of Secondary Endpoints

rwPFS, IC-TTP and Overall Survival will be summarized using Kaplan-Meier methods and displayed graphically. The 1/2/3/4/5-year rwPFS, IC-TTP and survival probability will be estimated using Kaplan-Meier methods and the 2-sided 95% CI will be provided. Potential influences of other demographic, baseline characteristics including biomarker profile use parametrical test, χ^2 or Fisher exact test. Objective Response Rate will be summarized for the SAT Population based on the investigator's assessment. The number and percent of subjects achieving objective response (CR or PR) will be summarized along with corresponding 2-sided 95% CI using the binomial distribution.

Intracranial Objective Response Rate will be summarized for the SAT Population based on the investigator's assessment. The assessment of intracranial response will be conducted on subjects with measurable and unmeasurable CNS metastases. The number and percent of subjects achieving objective response (CR or PR) will be summarized along with corresponding 2-sided 95% CI using the binomial distribution.

Subgroup analysis is considered to be conducted by baseline characteristics such as CNS (Yes/No), TP53 status (Yes/No), ALK-EML4 fusion variant (V1, V2, V3) in patients with baseline who receive lorlatinib in first line. Depending on the actual sample size at the time of analysis, adjustment by either combining or re-classifying the subgroups will be applied as needed.

Subgroup comparisons, where is applicable, will be performed using the Kaplan-Meier method and the log-rank test. Statistically significant level of $\alpha=0.05$ (two sides) is used for tests.

The qualitative exploratory endpoints will be categorized and summarized descriptively by count and percentage of patients. Missing data will be categorized by missing, unknown, or can't be determined.

The interim analysis will be performed when the completion of 2.5 year follow-up in late patient. The final full analysis will take place at the time of data cut-off (i.e. the completion of 60-month follow-up for all the participants).

Descriptive statistics will be used to summarize subject characteristics, study conduct, subject disposition, treatment administration/compliance, and safety parameters. Data will also be displayed graphically, where appropriate.

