initiation) in patients with previously untreated advanced ALK-positive NSCLC.²² At the time of first data cutoff, the mPFS was not reached (NR; 95% confidence interval [CI], NR=NR) in the lorlatinib group, as compared with 9.3 months (95% CI, 7.6-11.1) in the crizotinib group by BICR. The percentage of patients who were alive without disease progression at 12 months was 78% in the lorlatinib group and 39% in the crizotinib group (hazard ratio, 0.28, 95% CI, 0.19-0.41); $P < 0.001$, one-sided). The hazard ratio favored lorlatinib over crizotinib across all prespecified patient subgroups defined according to baseline characteristics and stratification factors. At the second data cutoff, the mPFS was yet NR (95% CI, NR-NR) in the lorlatinib group, as compared with 9.3 months (95% CI, 7.6-11.1 months) in the crizotinib group by BICR.²² 24-month and 36-month PFS rate were distinctly higher in the lorlatinib group of 68.2% and 63.5%, as compared with 21.5% and 18.9% in the crizotinib group (hazard ratio, 0.27, 95% CI, 0.184-0.388). For patients with measurable brain metastases at baseline, lorlatinib achieved 72% intracranial complete response (CR) rate, and 83% intracranial objective response rate (ORR). Time to intracranial progression by BICR was remarkably longer with lorlatinib than crizotinib in the intention-to-treat population as well as in patients with and without baseline brain metastases, in which 8 out of 37 patients with baseline brain metastases and only 1 out of 112 patients without baseline brain metastases had intracranial progression after median follow-up over 36 months. This indicates that lorlatinib possesses the potential to clear existing brain metastases, meanwhile prevents new metastatic lesions in the brain.

In consideration of high intracranial activity and 63.5% PFS rate and not reached mPFS after 36.7 months follow-up in the CROWN trial,²² ALK-positive NSCLC patients shall benefit most using lorlatinib in the first-line treatment in the clinical practice. Nevertheless, only 10 ALK+ NSCLC patients were randomized to the lorlatinib group in China mainland, and published data of clinical trials regarding first-line treatment of lorlatinib is still limited to CROWN trail. There is a vast vacancy of efficacy and safety regarding first-line lorlatinib treatment in China ALK-positive NSCLC patients. Further,

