After lorlatinib treatment for 4 weeks, patients will receive an imaging assess. The patients who achieve PR or SD with oligometastasis (refer to target lesions with residual disease, a maximum of 3 organs, and no more than 5 lesions in total) should continue lorlatinib treatment and will receive imaging assess per 8-12 weeks. If target lesions indicate stable in 2 consecutive imaging, investigators will organize MDT and comprehensively evaluate patients' will to decide and choose local therapy. The local therapy includes surgery, ablation and, radiotherapy et al. After local therapy, patients should continue taking lorlatinib. While those who achieve CR or with multiple metastasis will continue lorlatinib treatment without any local therapy.

To dynamically monitor ctDNA changes in ALK + NSCLC patients during Lorlatinib treatment; to explore the correlation between ctDNA and Lorlatinib treatment efficacy .Patients need check the ctDNA-seq (10000x) in plamsa with NGS at baseline,4weeks after lorlatinib treatment and at disease progression.

Subjects will be on lorlatinib therapy until disease progression or unacceptable toxicity, new systemic anticancer therapy instituted, withdrawal of consent, death, or investigator decision dictated by protocol compliance, whichever occurs first.

Patients received continuous daily PO dosing of lorlatinib 100mg QD with/without locally therapy, from the date of first dosing (per the current protocol) or until one of the following criteria were met (whichever occurred first): disease progression; initiation of a new anti-cancer therapy; unacceptable toxicities; global deterioration of health-related symptoms; pregnancy; withdrawal of consent; loss to follow-up; death; investigator decision dictated by protocol non-compliance; or study termination. Patients who have progressive disease (PD) (per RECIST v1.1, by investigator review) and for whom the investigator believes it is in their best interest to continue lorlatinib treatment are allowed to continue lorlatinib therapy, at the discretion of the investigator, until any alternate or additional systemic anti-cancer therapy regimen was implemented.

At the time of progression and termination of study treatment, the patients could receive

any therapy at the judgment of the investigator. This study will take 1 years to enroll subjects, and each subject will be followed up for survival status and subsequent cancer therapies up to 60 months from the date of first dosing.

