6.2.8 Long-term Follow-up for Progression and Survival

Subjects with no evidence of disease progression at the time of treatment discontinuation should be followed up until disease progression, regardless of any start of subsequent cancer therapy. Repeat tumor assessments are suggested approximately every 8-12 weeks from the date of CT/MRI at the end of study treatment.

All subjects (including those who show disease progression) must be followed up for subsequent cancer therapies and survival status regardless of the reasons for discontinuation from study drug treatment approximately every 2-3 months from post treatment follow-up visit. Telephone contact or other means to obtain timely regular follow-up is recommended, including subjects who are subsequently followed by providers other than the investigator. The information for subsequent therapies collected and recorded on the LinkDoc should include enumeration of subsequent treatment, including drugs administered, date of initiation and discontinuation of each medication. Each subject will be followed up for survival status and subsequent cancer therapies up to 60 months from the date of first dosing of lorlatinib.

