9.2 Effectiveness Analysis

9.2.1 Analysis Populations

The following subject populations will be assessed:

Safety-Analysis-Set (SAT) Population

The SAT Population will include all subjects who receive at least 1 dose of study medication. The SAT Population will be the primary population for evaluating treatment administration/compliance and safety.

Censoring for time-to-event efficacy endpoints (i.e., PFS and OS) will be elaborated in the SAT.

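### Kaplan-Meier for intracranial time to progression censors deaths, so the 1- to 5-year figures read as risks overstate intracranial progression, mainly at years 4 to 5 and with baseline brain metastases

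*Protocol*

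**What the plan says.** Section 9.2.4 of the protocol ends IC-TTP at "the date of the first documentation of objective progression of intracranial disease, based on either new brain metastases or progression of existing brain metastases". Neither death nor progression outside the brain is an event.

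Section 9.2.5 applies Kaplan-Meier to the IC-TTP curve and to its yearly values: "The 1/2/3/4/5-year rwPFS, IC-TTP and survival probability will be estimated using Kaplan-Meier methods", with two-sided 95% intervals. It also plans subgroup analysis by baseline CNS involvement (yes/no), using Kaplan-Meier and the log-rank test. No competing-risk method appears in the protocol.

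No censoring rule is given for IC-TTP. Section 9.2.1 says only that "Censoring for time-to-event efficacy endpoints (i.e., PFS and OS) will be elaborated in the SAT", which does not name IC-TTP.

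Two passages bear on what happens after extracranial progression:

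- Section 3.1: patients with progressive disease whom the investigator judges likely to benefit "are allowed to continue lorlatinib therapy, at the discretion of the investigator".
- Section 6.2.8: patients who stop treatment without progression "should be followed up until disease progression, regardless of any start of subsequent cancer therapy".

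Survival is followed "up to 60 months from the date of first dosing of lorlatinib".

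**The concern.** Kaplan-Meier assumes that a censored patient could still have the event later. A patient who has died cannot progress in the brain. With deaths censored, 1-KM describes intracranial progression if nobody died first, not the proportion of patients who actually have it.

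Sections 9.1 and 10.2 describe the study as descriptive, so the yearly percentages are themselves the result, and readers will take them as the risk that patients face in practice. Follow-up runs to 60 months and section 4.1 admits ECOG performance status up to 3, so some deaths without intracranial progression must be expected. The gap between 1-KM and the actual risk grows with time, and in absolute terms it is larger where the intracranial hazard is higher. The percentages in the CNS-yes and CNS-no groups are therefore affected unequally.

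**Working it through.** The protocol states no expected IC-TTP figure, and the sample size of about 100 is not derived from one, so there is nothing to reproduce. The check asks how large the overstatement could be.

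**Inputs**

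- Intracranial progression on lorlatinib in the cited phase 3 first-line trial (section 1): "8 out of 37 patients with baseline brain metastases and only 1 out of 112 patients without baseline brain metastases". That is 8/37 = 21.6%, 1/112 = 0.9%, and 9/149 = 6.0% overall, after a median follow-up of more than 36 months.
- 36-month PFS on lorlatinib in the same trial (section 1): 63.5%.
- 5-year probability of death without intracranial progression: **assumed**, 10% to 50%. The protocol gives no figure.

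**Model.** Constant monthly hazards: h for intracranial progression and c for the competing event.

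- 1-KM(t) = 1 - exp(-h·t)
- Cumulative incidence CIF(t) = h/(h+c) × [1 - exp(-(h+c)·t)]

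**Case A: only death competes.** Set c = -ln(1-d)/60 for 5-year mortality d, and solve for h so that CIF(36) equals the observed proportion.

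| Group | d | c | h | 1-KM, 5 y | CIF, 5 y | Excess (points) |
|---|---|---|---|---|---|---|
| All (9/149) | 10% | 0.00176 | 0.00179 | 10.2% | 9.7% | 0.5 |
| All | 30% | 0.00594 | 0.00193 | 10.9% | 9.2% | 1.7 |
| All | 50% | 0.01155 | 0.00213 | 12.0% | 8.7% | 3.3 |
| Brain metastases (8/37) | 10% | 0.00176 | 0.00700 | 34.3% | 32.7% | 1.6 |
| Brain metastases | 30% | 0.00594 | 0.00759 | 36.6% | 31.2% | 5.4 |
| Brain metastases | 50% | 0.01155 | 0.00842 | 39.7% | 29.4% | 10.2 |

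Without baseline brain metastases (1/112) the 5-year excess is 0.1 to 0.5 points over the same range. At 30% mortality the CNS-yes minus CNS-no difference at 5 years is 36.6 - 1.7 = 34.9 points by 1-KM and 31.2 - 1.4 = 29.8 points by cumulative incidence.

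**Case B: extracranial progression is censored as well (not stated in the protocol).** The total hazard comes from PFS: -ln(0.635)/36 = 0.01261. The intracranial share is f = 0.0604/0.365 = 0.165, so h = 0.00209 and c = 0.01053. At 60 months event-free survival is 0.635^(60/36) = 0.469. Then:

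- 1-KM = 1 - 0.469^0.165 = 11.8%
- CIF = 0.165 × (1 - 0.469) = 8.8%
- excess 3.0 points, about one third in relative terms (11.8/8.8 = 1.34)

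| Year | 1-KM | CIF | Excess (points) |
|---|---|---|---|
| 1 | 2.5% | 2.3% | 0.1 |
| 2 | 4.9% | 4.3% | 0.6 |
| 3 | 7.2% | 6.0% | 1.2 |
| 4 | 9.5% | 7.5% | 2.0 |
| 5 | 11.8% | 8.8% | 3.0 |

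Excesses are taken before rounding. A simulation with 100 patients per run and 3,000 runs gave the same 5-year values (11.8% and 8.8%).

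For patients with baseline brain metastases, assuming the overall PFS applies to them, f = 0.216/0.365 = 0.592 and the 5-year values are 36.1% and 31.4%, an excess of 4.7 points. With 36-month PFS assumed at 50% they are 39.3% and 29.6%, an excess of 9.7 points.

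**The case against.** Kaplan-Meier is a common and legitimate net summary of time to progression, and section 9.2.5 never says that 1-KM is the proportion of patients affected. This is one secondary endpoint in a study that section 10.2 limits to description. Overall, the possible bias is smaller than the sampling error: at 8.8% with 100 patients the 95% half-width is 1.96 × √(0.088 × 0.912/100) = 5.5 points. All of this stands and limits the severity. It does not remove the point, because in a descriptive report the 1- to 5-year percentages will be read as risks.

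Three stronger readings are tempting, and the protocol does not support them.

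- *Extracranial progression is censored under the plan.* No passage says so. Section 6.2.8's follow-up until progression concerns only patients who stopped treatment without it. Section 3.1 allows lorlatinib after progression, and the scans in section 6.2.5 include the brain. Case B is therefore conditional. Its 8.8% is also the incidence of the brain as first site of failure, not the share who ever progress there, because a patient with extracranial progression can still progress in the brain.
- *Patients with brain metastases are worse affected because they have more competing events.* The protocol gives no PFS or mortality by stratum. If the overall PFS applied to them, their competing events by 36 months would be 36.5% - 21.6% = 14.9%, against 36.5% - 6.0% = 30.5% overall. Their larger absolute excess follows from the higher intracranial hazard alone.
- *The CNS yes/no test is invalid.* The log-rank test compares cause-specific hazards and remains valid for that purpose when competing events are censored. Only the accompanying percentages mislead.

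**Conclusion.** The point holds, at minor to moderate weight. The event definition and the estimator are both written in the protocol, so this is a method it fixes, not a detail left to an analysis plan. The direction is certain: once deaths without intracranial progression occur ahead of later intracranial events, 1-KM exceeds the actual probability.

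The size depends on assumptions. With death alone competing, the 5-year excess is about 0.5 to 3.3 points overall and 1.6 to 10.2 points with baseline brain metastases, for assumed 5-year mortality of 10% to 50%. If extracranial progression were also censored, the overall excess would be negligible at 1 year, 1.2 points at 3 years and 3.0 at 5 years. The issue matters mainly at years 4 to 5 and in patients with baseline brain metastases.

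The figures assume constant hazards carried forward to 60 months and treat crude counts from the cited trial as 36-month cumulative incidences. Case B further assumes that each intracranial progression was the first PFS event.

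**What to change.** In section 9.2.5, take IC-TTP out of the sentence on yearly Kaplan-Meier probabilities and add wording such as: *The 1-, 2-, 3-, 4- and 5-year cumulative incidence of intracranial progression will be estimated by the Aalen-Johansen method with 95% confidence intervals, overall and by baseline CNS status, with death without intracranial progression as the competing event.*

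State how extracranial progression is handled, and do not make it a competing event. Where brain imaging continues, keep following the patient for intracranial progression; where it stops, censor at the last brain assessment. Say also how the start of new systemic therapy is treated. Incidence by first site of progression can be reported, but only as a separately labelled analysis.

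Kaplan-Meier can stay as a supplementary net summary for comparison with publications that used it, and the log-rank test can stay for the subgroup comparison.

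The cost is a few sentences and one extra analysis. Section 3.1 already lists survival status and lesion location among the data collected.

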9. DATA ANALYSIS/STATISTICAL METHODS

9.1 Sample Size Determination

The primary objective of this real-world study is to demonstrate that locally therapy during 1L lorlatinib is instrumental in prolonging TTD by investigator assessment per RECIST v1.1.

Approximately 100 patients who receive lorlatinib in first line are expected to be included in this study. Since this study is descriptive without specified hypothesis, the sample size is not determined based on statistical assumptions, but according to the following information: epidemiology, China marketing competition environment, marketing research report, drug availability, patient affordability, health insurance coverage, and at least 20% dropout rate. Comprehensively, the final sample size of this study is expected to reach for about 100 cases.

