9.2.3 Analysis of Primary Endpoint

TTD will be summarized using Kaplan-Meier methods and displayed graphically. Potential influences of other demographic baseline characteristics including biomarker profile use parametrical test, χ^2 or Fisher exact test .

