will be done for each site to validate generalizability of outcomes respective of geographic location of the participants. Furthermore, disease assessment will be based on evaluations performed by the attending physicians in real-world clinical practice. Although a significant proportion of physicians use RECIST in their clinical practice, it may still result in an inconsistent definition of tumor response and disease progression. Such information bias can be minimized to some extent by following a well-designed data management process and through appropriated definition of variables to sufficiently use available information. Lastly, no hypotheses will be tested in this study and only descriptive analysis will be performed. Thus, results cannot serve as a general conclusion on the effectiveness and safety of lorlatinib.

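### Section 9.2.5 plans subgroup log-rank tests at a two-sided 0.05 level, while Section 10.2 says that no hypotheses will be tested

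*Protocol*

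**What the plan says.** Protocol Section 9.2.5 names the subgroup factors: "Subgroup analysis is considered to be conducted by baseline characteristics such as CNS (Yes/No), TP53 status (Yes/No), ALK-EML4 fusion variant (V1, V2, V3". The factors are introduced as examples, so the list is open. Categories may be combined or redefined depending on the sample size reached. The section then states: "Subgroup comparisons, where is applicable, will be performed using the Kaplan-Meier method and the log-rank test", followed by: "Statistically significant level of $\alpha=0.05$ (two sides) is used for tests".

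Sections 9.2.3 (primary endpoint) and 9.2.5 (secondary endpoints) each add that potential influences of baseline characteristics, including the biomarker profile, will be examined with a parametric test, chi-square or Fisher exact test.

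Two other places describe a study without tests. Section 9.1 gives as its reason for not calculating a sample size: "Since this study is descriptive without specified hypothesis". The limitations text under Section 10.2 says: "no hypotheses will be tested in this study and only descriptive analysis will be performed".

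**The concern.** A log-rank test judged against a declared significance level is a hypothesis test. The same holds for a chi-square, Fisher or parametric test used to decide whether a baseline factor influences an outcome. Sections 9.2.3 and 9.2.5 therefore plan what Section 10.2 says will not be done.

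What is at stake is the status of the biomarker results. Section 2.1 lists the association of effectiveness with brain metastases, fusion variant and TP53 among the secondary objectives, with the molecular factors depending on what the medical records hold. About 100 patients will be split by these factors, so some groups will be small. An author following 9.2.5 could report a subgroup difference at p below 0.05 as statistically significant. An author following 10.2 could not. The protocol does not say which section governs.

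**Working it through.** **Setting the sections side by side**

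| Section | What it provides |
|---|---|
| 9.2.5 | Log-rank subgroup comparisons, with a two-sided 0.05 level for tests |
| 9.2.3 and 9.2.5 | Parametric, chi-square or Fisher tests of baseline and biomarker influences |
| 10.2 | No hypotheses tested, descriptive analysis only |
| 9.1 | Descriptive study without a specified hypothesis |

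The first two rows conflict directly with the third. The fourth row is weaker support, because it is given as a reason for having no formal sample-size calculation.

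**Size of the issue.** The protocol states no number of tests and no overall error rate, so there is no figure to reproduce. What follows is an illustration.

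Inputs from the protocol:
- Level per test: 0.05, two-sided (9.2.5).
- Named factors: 3, namely CNS, TP53 and fusion variant (9.2.5).
- Secondary time-to-event endpoints: 3, from "rwPFS, IC-TTP and Overall Survival will be summarized using Kaplan-Meier methods and displayed graphically" (9.2.5).
- A possible fourth endpoint is TTD. Section 9.2.3 says "TTD will be summarized using Kaplan-Meier methods and displayed graphically" and mentions no log-rank test, so including TTD is an assumption.

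Assumptions not in the protocol: each factor is tested once on each endpoint, every null hypothesis is true, the factors are independent of one another, and the endpoints within a factor share a common correlation.

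*Independent tests.* P(at least one p < 0.05) = 1 − 0.95^k.
- One endpoint, k = 3: 1 − 0.95^3 = 14.3%.
- Three endpoints, k = 3 × 3 = 9: 1 − 0.95^9 = 37.0%.
- Four endpoints, k = 3 × 4 = 12: 1 − 0.95^12 = 46.0%.

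*Correlated endpoints.* The endpoints are measured in the same patients, so positive correlation is expected. A simulation of 400,000 null draws used 1-df statistics for CNS and TP53 and a 2-df statistic for the three-level variant. It gave:

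| Correlation between endpoints | 9 tests | 12 tests |
|---|---|---|
| 0.3 | 35.5% | 43.7% |
| 0.5 | 33.3% | 40.0% |
| 0.7 | 29.4% | 34.4% |
| 0.9 | 23.2% | 25.8% |

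Over 9 to 12 tests and correlations of 0 to 0.9, the range is therefore about 23% to 46%.

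*One pair is not a plausible null.* Section 1 reports intracranial progression on first-line lorlatinib in the CROWN trial in 8 of 37 patients with baseline brain metastases (8/37 = 21.6%) and in 1 of 112 without (1/112 = 0.9%). A significant difference in IC-TTP by CNS status would probably be true. Dropping that one test gives, under independence, 1 − 0.95^8 = 33.7% and 1 − 0.95^11 = 43.1%. The illustration falls by about 3 percentage points, and its order of magnitude does not change.

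**The case against.** The strongest case on the other side is that little depends on these tests. Section 2.1 words the biomarker aim as exploration. Section 9.2.5 says only that subgroup analysis is considered, and that comparisons are made where applicable. Section 10.2 adds that the results cannot support a general conclusion on effectiveness and safety. Neither the sample size nor the primary analysis rests on a subgroup p-value, and nominal p-values for exploratory subgroups in a descriptive cohort are ordinary practice. All of this stands, and it limits the severity. It does not remove the conflict: if the aim is exploratory, the significance threshold has no role.

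A reader might infer three stronger points that the document does not support.
- **That the plan carries a 46% false-positive rate.** That figure needs 12 tests and independence, and the protocol states neither. The reading closest to 9.2.5 is 9 tests, and correlation lowers the rate further.
- **That subgroups may be redrawn after the outcomes are seen.** Section 9.2.5 ties regrouping to the sample size reached, not to results. Pooling sparse categories on size alone does not inflate the type I error.
- **That the absence of a multiplicity procedure is itself a defect.** The protocol may properly leave that to a statistical analysis plan, which is not shown here. Such a plan could add detail but would not remove the contradiction within the protocol.

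**Conclusion.** The contradiction holds. Section 9.2.5 sets a significance level for subgroup log-rank tests, and Sections 9.2.3 and 9.2.5 plan further tests of baseline and biomarker influences, while Section 10.2 says that nothing will be tested. Read literally, 9.2.5 permits significance claims that 10.2 disclaims.

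The figure of about 23% to 46% for at least one false positive is illustrative only and should always be quoted with the assumptions behind it. The top of the range is not the plan's error rate. Further factors, pairwise variant contrasts or repeated analyses would raise the figure, but the protocol does not commit to any of these for the subgroup tests. Even the low end is more than four times the nominal level (23.2/5 = 4.6).

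Severity is minor to moderate: the point affects how subgroup results may be described, not the primary Kaplan-Meier summary of TTD.

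**What to change.** 1. In Section 9.2.5, delete the sentence that sets the 0.05 significance level.
2. In the same section, state that subgroup results will be reported as Kaplan-Meier curves with hazard ratios and 95% confidence intervals, labelled exploratory.
3. In both 9.2.3 and 9.2.5, state that any p-values kept (log-rank, parametric, chi-square or Fisher) are nominal and support no claim of significance. Changing only the log-rank text would leave the other tests in the same conflict.
4. Align Sections 9.1 and 10.2 with this wording. If nominal p-values are kept, the limitations text should say so.

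The cost is wording only, with no effect on enrolment, data collection or follow-up. The downside is that subgroup results can no longer be called statistically significant.
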